- A. One recruitment strategy will be to contact people off of a pre-specified list of people receiving peer to peer support or on the wait list to receive peer to peer support. These people are already receiving community services from Community Place. We will send out letters to the first 10 people on the list. The letter will give them the option to call us but it will also let them know that we will be calling them within the next two weeks to see if they are interested in participating in the research study. Research staff will select the next person to call and recruit to the study in the recruitment pattern according to the matching strategy that the biostatisticians prepared based on the sociodemographic breakdown of the clientele that are currently receiving peer to peer support. We will send out the *Introductory Letter* to potential participants on the wait list and to potential participants currently receiving peer to peer support. We will send out eligibility letters to people enrolled in peer-to-peer support and on the wait list simultaneously. Every 2-3 weeks we will send letters to 10 new people.
- B. A second recruitment strategy will be by making an announcement about the study at monthly training meetings for both Foster grandparent and senior companion programs. After the announcement is made, the research coordinator will approach potential participants at monthly training meetings and ask them if they are interested in learning more. If interested, we will tell them about the study, screen them for eligibility send them home with a consent form and set up a time to conduct the baseline interview. There is the possibility of enrolling 15-20 people at this meeting. This meeting occurs every month.
- C. A third recruitment strategy will be to hold informational sessions for the purpose of recruiting eligible participants for the study creating our "waitlist". These sessions will be held at community centers around town and in other venues where older adults frequent.

D. Community Place will be partnering with Star Program to recruit additional peers.

Recruitment Goal: As of February 23, 2016 the new recruitment goal at Community Place will be to recruit 226 participants into the study (113 experimental and 113 control)

Alpert Jewish Family and Children's Service

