The Alpert Jewish Family and Children's Service, West Palm Beach currently serves approximately 205 people who receive peer to peer support. There is not currently a waiting list so we will be recruiting people out of the community to serve as the control group. All people in both groups have access to all other services that the Jewish Family and Children's Service offers older adults in the community. People receiving peer to peer support will receive ID Numbers PB100E to PB499E and people receiving standard community services (on the wait list to receive peer to peer support) will receive ID numbers PB500C to PB999C.

A list of participants that are currently receiving peer to peer support will be uploaded into DatStat. However, only first name, age, date of birth, gender and race will be uploaded into the system. The Research Staff will keep a separate list of contact information for these participants on a secure file on her computer. Once a participant agrees to be in the study, then the additional contact information (phone number, address, last name) will be added into DatStat.

- A. One recruitment strategy will be to contact people off of a pre-specified list of people receiving peer to peer support. These people are already receiving services from the Jewish Family and Children's Service. We will send out letters to the first 10 people on the list. The letter will give them the option to call us but it will also let them know that we will be calling them within the next two weeks to see if they are interested in participating in the research study. Research staff will select the next person to call based on the number of people they are trying to recruit in each of the pre-specified categories (ex: white women 65-70). The biostatisticians have created a list of the number of people we should recruit in each demographic bucket based on the demographic breakdown of the people currently receiving peer to peer support. We will then send out the *Introductory Letter* to potential participants from the sessions (on the "wait list") and to potential participants currently receiving peer to peer support. We will send out eligibility letters to people enrolled in peer-to-peer support and to those who are eligible for peer to peer services simultaneously. Every 2-3 weeks we will send letters to 20 new people.

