We will call back in one week for our second attempt and leave the same message. On the third phone call attempt one week later, we will leave the following message.

Hello {U:DATSTAT_FIRSTNAME}. My name is {U:RA_FIRST} {U:RA_LAST} from {U:DATSTAT_SITE}. I was calling again to see if you would like to participate in the research study about helping older adults stay in their homes and communities. If you are interested in learning more about the Aging in Place study please call me back at {U:RA_TELEPHONE} and leave me a message if I'm not at my desk. I will not be reaching out to you again about this study. Again, my name is [U:RA_FIRST] and my phone number is [U:RA_TELEPHONE] and I hope to talk with you soon. Have a great day.

After the third failed attempt, we will send them the *Letter after 3rd attempt Failed Recruitment Control* or *Letter after 3rd attempt Failed Recruitment Experimental*. All attempts to contact a participant will be documented in DatStat with outcome of the call.

If the research staff talks with a participant but “now is not a good time” then the research staff and the potential participant should set up a better time to talk, whether that is tomorrow or next month. In this situation, the research staff should consider this contact attempt still open (i.e. if this is the first attempt than the first attempt stays open). It is only when you don't reach a participant that the contact attempt closes and we move on to the next contact attempt.

The first time the research staff successfully connects with a participant in person or via the telephone they will follow the screening script outlined in the screening survey.

Inclusion & Exclusion Criteria

Inclusion Criteria

- ≥ 65
- Eligible for peer to peer companion services
- Living independently or in independent care

Exclusion Criteria

- Receives > 40 hours of in home care from someone other than spouse
- Has plans to move to a higher level of care in the next year
- Has a score on the telephone interview of cognitive status (TICS) ≤ 25
- Doesn't live permanently in one location “snow birds”

If in the peer to peer group the following exclusion criteria also apply

- *Utilization of a peer companion is temporary*
- *Primary reason older adult has a peer companion is to provide respite for their caregiver*

Matching

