For Community Place and Alpert Jewish Family and Children's Service (AJFCS), we are matching participants on the following characteristics: age group (<70, 70-80, and ≥ 80 years), gender (male and female), race/ethnicity (African American, Hispanic, and non-Hispanic White) and at Community Place we are also matching based on County (Monroe or Livingston).

At both all sites we are going to recruit people from the waiting list and match them with people already receiving peer to peer services. Every month research staff at UW will ask to see the matching spreadsheet as a way to monitor how matching is progressing at each site.

Enrolling more than one person per household (added 1/14/2016)

As of February 22, 2016, we will only enroll one person per household. This is the protocol for determining which person from the household we will enroll.

- a. If Participant A is enrolled in the study (signed the consent form) and they say they would like their partner would like to participate, the research staff person will let them know that according to study protocol we are only allowed to enroll one person per household. Participant A will be the person that is enrolled in the study.
- b. If prior to enrollment a study staff person is informed that both partners in a couple want to participate in the study. The staff person will let the two participants know that we can only enroll one participant from the couple. If we only need one person then the research staff will screen and enroll that person.
- c. If we know in advance there is a couple interested in participating and both people are needed for the study then we will randomly select one person per household. In this case you should screen both participants. If both participants are deemed eligible to participate you should first assign one participant heads and one participant tails. Then you should pull out the randomization envelope and open it. This envelope will tell you which participant you will enroll. At this time you will discard the envelope.

Enrollment in Study

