Randomization and matching In order to reduce potential bias further, participants from the AJFCS of Palm Beach will be allocated either to peer-to-peer support (Intervention) or standard community support (Control) in a 1:1 ratio using permuted block randomization, stratified by age, gender and race/ethnicity. Barring randomization in JFS of LA and Community Place of Greater Rochester, older adults already participating in peer-to-peer support and those on the waiting list will be matched on age, gender and race/ethnicity to mitigate potential differences between the two groups. In order to avoid reporting/ascertainment bias, calls will be made to all participating older adults and support staff at 3 and 9 months as outlined in Figure 4 above.

Sample Size Justification Given the total sample size of 720 at-risk older adults, the study has 0.80/0.85/0.90 power to detect the effect size of 0.209/0.223/0.242 for the primary outcome measure of the annualized rate of hospitalization, ED use and institutionalization at a two-tailed significance level 0.05. The effect size here is defined as the difference in the mean annualized rate of hospitalization, ED use and institutionalization between the two groups divided by the standard deviation of the annualized rate assumed to be common in the two groups. Due to random drop-out or loss to competing event of death, the study will have less power to detect the stated effect sizes or will have the stated power for larger effect sizes.

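### Temporary users and caregiver-respite clients are excluded from the peer group only, so wait-listed controls may include a type of person the peer group leaves out; the direction and size of any bias are unknown

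*Protocol*

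**What the plan says.** **Eligibility.** Protocol, Inclusion & Exclusion Criteria, sets common criteria for both groups, including "Eligible for peer to peer companion services". It then continues: "If in the peer to peer group the following exclusion criteria also apply". The two added criteria are "Utilization of a peer companion is temporary" and "Primary reason older adult has a peer companion is to provide respite for their caregiver". Nothing equivalent is stated for controls.

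**Source of controls.** At Community Place and Jewish Family Service of LA, the first recruitment route is a "pre-specified list of people receiving peer to peer support or on the wait list to receive peer to peer support". Both sites also recruit elsewhere: information sessions at Community Place, and Park LaBrea or meal programs at LA. For Alpert Jewish Family and Children's Service (AJFCS) the protocol says: "There is not currently a waiting list so we will be recruiting people out of the community to serve as the control group". The Matching section nevertheless says "At both all sites we are going to recruit people from the waiting list".

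**Matching and analysis.** The SAP (Randomization and matching) says that at LA and Community Place "older adults already participating in peer-to-peer support and those on the waiting list will be matched on age, gender and race/ethnicity". The protocol's Matching section adds county at Community Place. The SAP's Analysis Plan makes unadjusted two-sample tests primary. Regression follows, adjusting for stratification factors, site and other confounders that it does not name.

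**The concern.** The two added criteria select on why, and for how long, a person needs a companion. If that is related to hospital use, emergency visits or institutionalization, filtering one group on it and not the other makes the groups differ before any effect of peer support. The opening of the SAP's Statistical Considerations says the sampling plan is meant to make the groups comparable although not everyone can be randomized. A one-sided filter works against that aim. At Community Place and LA there is no randomization to fall back on.

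What is at stake is a shift in the primary comparison that the stated design neither measures nor removes. It could create an apparent benefit or hide a real one.

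**Working it through.** **1. Does anything else in the plan remove the difference?**

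- *Common exclusions.* The limit on in-home care (over 40 hours, not counting a spouse) concerns the amount of care, not the reason for or duration of companion use. Someone cared for mainly by a spouse who needs respite passes it. The rules on planned moves and on the cognitive score do not address the point either.
- *Matching.* Age group, gender, race/ethnicity, and county at Community Place. Reason and duration are not matched.
- *Primary analysis.* Unadjusted.
- *Secondary regression.* It could include reason and duration under its unnamed confounders, but only if they are recorded, and the documents supplied do not say that they are.

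So nothing stated removes it.

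**2. Reproducing the plan's own figure.** Inputs from the SAP, Sample Size Justification: N = 720, taken as 360 per group, two-sided alpha 0.05, effect in SD units.

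- Standard error of the difference = √(2/360) = 0.0745 SD.
- Detectable effect at 80% power = (1.960 + 0.842) × 0.0745 = 0.209 SD, as stated. The figures for 85% and 90% power also reproduce (0.223 and 0.242).

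**3. Illustrative size of the shift.** The documents give no share of such people, no event rate for them, and no mean or SD of the annualized rate. All of the following are assumptions:

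- share of controls of this type, p = 0.05 to 0.15;
- their event rate relative to other controls, r = 1.5 to 2;
- mean of the other controls, 1 event a year; SD = √(1 + 1²) = 1.414 (overdispersed count with dispersion 1).

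Control mean = 1 × [(1 − p) + p·r], so the shift is p(r − 1) events a year, or p(r − 1)/1.414 in SD units.

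- Low: 0.05 × 0.5 = 0.025; 0.025/1.414 = 0.018 SD.
- High: 0.15 × 1 = 0.15; 0.15/1.414 = 0.106 SD.

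If r is below 1, the sign reverses.

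**4. Pooling over sites.** Planned controls under the site goals in the protocol: Community Place 113, AJFCS 150, LA 30, total 293. Outside AJFCS: 113 + 30 = 143, and 143/293 = 0.488. If only these controls are affected:

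- Low: 0.018 × 0.488 = 0.009 SD.
- High: 0.106 × 0.488 = 0.052 SD.

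| Assumption | Shift among affected controls | Pooled, 143 of 293 | Pooled shift ÷ 0.209 |
|---|---|---|---|
| p = 0.05, r = 1.5 | 0.018 SD | 0.009 SD | 4% |
| p = 0.15, r = 2 | 0.106 SD | 0.052 SD | 25% |

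The 143 is an upper limit for wait-listed controls, because some people at these two sites come from other routes.

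**5. What a pooled shift near the top of that range would do.** Take 0.05 SD at 360 per group; 0.05/0.0745 = 0.671.

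- With no true effect, the chance of a significant result is Φ(0.671 − 1.960) + Φ(−0.671 − 1.960) = 0.103, against a nominal 0.05.
- If the shift instead works against a true effect of 0.209 SD, power is Φ((0.209 − 0.05)/0.0745 − 1.960) = 0.57, against 0.80.

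At the low end (0.009 SD) the false-positive rate stays at about 5%.

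**The case against.** **The criteria describe a companion already in place.** This is the strongest point. Temporary use can be read as defining exposure: it keeps short-term users out of a group followed for a year. A control has no use to classify and can only be asked about intended use, which may not pick out the same people. This stands as a limit on the remedy. It explains the respite criterion less well, since that concerns the type of client rather than the length of exposure. Whatever the motive, one group is filtered and the other is not.

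**The direction is not known.** A reader might infer that dependent or acutely ill people accumulate among controls, so that the comparison favours peer support. The documents do not support that. They say nothing about the health of respite or temporary clients. A temporary user may be recovering and a respite client has an engaged caregiver, so either could have fewer events. The common exclusions also trim the most dependent people from both groups.

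**The scope is narrower than all controls.** A reader might apply the shift to every control. The question has clear meaning only for people waiting for a companion, at most 143 of 293 planned controls. For community recruits it is hypothetical.

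**It may be partly handled already.** The screening survey that the protocol refers to is not among the documents and may ask about need. The secondary regression may adjust for it. Both are possible; neither is stated.

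**Conclusion.** The asymmetry is explicit, and no stated criterion, matching factor or primary analysis removes it. Wait-listed controls at Community Place and LA may include people of a type excluded from the peer group. The bias could go either way, and its size cannot be determined from the documents. On the assumed shares and event-rate ratios, it runs from negligible (0.01 SD pooled) to about a quarter of the design effect (0.05 SD pooled). That range rests entirely on assumed inputs and on sites contributing in proportion to their recruitment goals. It is worth correcting because the remedy is cheap, but it does not show that a favourable result would be spurious.

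A related inconsistency needs reconciling. The SAP describes AJFCS as randomized 1:1. The protocol's AJFCS and Matching sections describe existing recipients matched to recruited controls. If screening precedes randomization there, a group-specific exclusion cannot work as written.

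**What to change.** 1. **Wait-listed controls still to be enrolled (Community Place, LA).** At screening, ask the main reason for wanting a companion and whether the need is expected to be temporary. Apply exclusions parallel to the peer-group criteria from then on.
2. **Wait-listed controls already enrolled.** Record the answers and keep everyone in the main analysis. Prespecify a sensitivity analysis of the main comparison without those who would have been excluded. Making the reduced set the main comparison would be a post-enrolment exclusion in one group, based on retrospective answers.
3. **Controls not from a wait list (AJFCS, information sessions, Park LaBrea, meal programs).** Record the answers only.
4. **AJFCS.** Reconcile the two descriptions of allocation, and state when screening occurs relative to it and how the two criteria then apply.

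**Cost.** Two extra screening items, and imperfect equivalence between intended and actual use. The loss of eligible controls is small at Community Place, with 408 on the list for a goal of 113. LA is tightest: 35 are wait-listed for a goal of 30, and losing 15% leaves 35 × 0.85 ≈ 30 before any refusals, other exclusions or matching losses. LA's other recruitment routes may then have to supply more of its controls.

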Appendix	
Introductory Letter for Participants (Community Place, AJFCS, JFS of LA)	
Failed Contact Recruitment Letter (Community Place)	
Reminder Letter (Community Place, AJFCS)	
Failed Contact 3, 6, 9, 12 month data collection (Community Place)	

Recruitment Strategies

Community Place

Community Place currently has 210 people receiving peer to peer support and 408 people on the wait list to receive peer to peer support. These numbers are fluid. All people in both groups have access to all other services that community place offers older adults in their community such as access to the Senior Center, various services we can connect with through our caseworker (Home delivered meals, benefits eligibility, Catholic Family Center-Elder one, Food link, Clothing services, legal consulting services, and Life span (Financial Budgeting, caregivers plan, HEP, High Cap-Health Insurance, Elder abuse prevention, and Rep pay program)).

All the people that are in the correct age range (≥ 65 years old) and have no known cognitive impairment will be uploaded into the study database in DatStat. People receiving peer to peer support will receive ID Numbers R100E to R499E and people receiving standard community services (on the wait list to receive peer to peer support) will receive ID numbers R500C to R999C. The following variables or a subset of these variables will be uploaded for all participants: ID, First Name, Last Name, Mailing Address, Phone, Age, Date of birth, gender, race, language preference, P2P program type, peer companion name, study group, RA first name, RA last name, RA telephone, RA email, Site PI.

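### The eligibility criteria and the one-per-household rule do not prevent a control from living with a current peer-support recipient, so any benefit a companion brings to the home could dilute the comparison.

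*Protocol*

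**What the plan says.** **Household rule** (Protocol, Enrolling more than one person per household). From 22 February 2016 one person per home is enrolled, under three cases.
- (a) A participant who has already consented stays, and the partner is turned away.
- (b) Where a couple comes forward before enrolment and the study can use just one of them: "If we only need one person then the research staff will screen and enroll that person".
- (c) Where the couple is known in advance and "both people are needed for the study then we will randomly select one person per household", both are screened and, if both are eligible, a sealed envelope picks one.

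**Eligibility** (Protocol, Inclusion & Exclusion Criteria). The exclusions for everyone concern hours of in-home care, plans to move to more care, cognitive score and part-year residence. Two further exclusions concern the companion: temporary use, and a companion whose main purpose is caregiver respite. Both apply only to the peer-support group.

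**Source of the groups** (Protocol, Recruitment Strategies and Matching). The intervention group is drawn from current recipients and the controls from waiting lists or the local community. Community Place reports 210 recipients and 408 people waiting. The Los Angeles agency reports 57 and 35.

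**Analysis** (SAP, Analysis Plan and Sample Size Justification). No household variable, measure of control exposure or related sensitivity analysis is described. The power statement names drop-out and death as causes of lost power, without figures.

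**The concern.** Limiting enrolment per home is not the same as limiting exposure per home. A control may have a spouse or housemate who is visited by a companion. That control could share the company, the practical help or the relief from caregiving, yet would be analysed as receiving standard services only.

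The gap is wider than couples who both volunteer. A recipient who is not interested, or who fails the cognitive or care-hours criterion, can have a companion at home while an eligible co-resident enters as a control. The protocol's own respite exclusion recognises that a companion can serve someone other than the named recipient, but it operates only on the recipient's side.

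At stake is a bias toward no difference that longer follow-up or a larger sample would not remove, and that the supplied text has no means of detecting.

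**Working it through.** **Step 1. What the text allows.** Take a home with one current recipient and one eligible non-recipient.
- Under (a), if the non-recipient has already consented as a control, that person stays in the study whatever the partner receives.
- Under (b), if only a control is needed, the non-recipient is enrolled.
- Under (c), if both are needed and both are eligible, the non-recipient is enrolled with probability one half.
- If the recipient never comes forward, none of the three cases applies and the non-recipient is screened like anyone else.

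No listed criterion removes the control in any of these paths. The supplied text also shows no household limit before 22 February 2016.

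**Step 2. Reproduce the plan's power.** Inputs from the SAP, Sample Size Justification: "Given the total sample size of 720 at-risk older adults"; "the study has 0.80/0.85/0.90 power to detect the effect size of 0.209/0.223/0.242"; testing "at a two-tailed significance level 0.05". The effect is in SD units, being the mean difference "divided by the standard deviation of the annualized rate assumed to be common in the two groups". I take 360 per group: the SAP states allocation "in a 1:1 ratio using permuted block randomization" for the Palm Beach site, and the protocol's site goals are equal by arm.

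Power = Φ(δ√(n/2) − 1.960), with n = 360 and √180 = 13.416.
- δ = 0.209: Φ(2.804 − 1.960) = 0.801
- δ = 0.223: Φ(2.992 − 1.960) = 0.849
- δ = 0.242: Φ(3.247 − 1.960) = 0.901

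The stated figures reproduce.

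**Step 3. Dilution.** Let f be the share of controls living with a recipient, and s the fraction of the full effect that reaches them. Neither is in the documents; both are assumptions. With the SD unchanged, the diluted effect is δ(1 − f·s), and the sample-size factor that restores power is 1/(1 − f·s)². Starting from δ = 0.209 and N = 720:

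| f (assumed) | s (assumed) | f·s | Diluted effect | Power | Factor | Total N for 80% |
|---|---|---|---|---|---|---|
| 0 | – | 0 | 0.209 | 0.801 | 1.000 | 720 |
| 1% | 50% | 0.5% | 0.208 | 0.797 | 1.010 | 726 |
| 5% | 50% | 2.5% | 0.204 | 0.781 | 1.052 | 758 |
| 10% | 50% | 5% | 0.199 | 0.759 | 1.108 | 798 |
| 10% | 100% | 10% | 0.188 | 0.714 | 1.235 | 888 |

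Only the product f·s matters. The loss stays within about 2 power points unless f·s exceeds about 2.5%.

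**Step 4. Sensitivity to sample size.** The protocol's site goals sum to 226 + 300 + 60 = 586, not 720. With 293 per group, power at δ = 0.209 starts at 0.716 and becomes 0.711, 0.694 and 0.671 for f·s of 0.5%, 2.5% and 5%. The loss from dilution is of similar size.

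**The case against.** The strongest reply is that the documents show permission, not occurrence. They report no home with one recipient and one control, and they do not say that a companion's visits help a co-resident. Case (c) does not say that the two partners belong to different groups; both could be waiting or both could be recipients. A reader might infer that some controls are in fact exposed from the start and that the estimate is therefore diluted. The documents do not support that reading. This objection stands, and the point has to be conditional.

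Second, the screening and baseline surveys are cited but not supplied. Either may ask about living arrangements or companion contact, so one cannot conclude that exposure would go unrecorded. Nor do the documents say how agencies judge service eligibility for the co-resident of a recipient. This also stands.

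Third, staff may correct the study group before consent (Protocol, Updating or changing participant information once enrolled in study), so a person found to be sharing a companion could be reassigned. That helps only if someone notices; it is not a systematic check.

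Fourth, address matching is not free. The Community Place upload list includes "ID, First Name, Last Name, Mailing Address, Phone, Age, Date of birth", but the protocol allows a subset of those fields to be uploaded. The Palm Beach site keeps recipients' contact details outside the study database until they agree to join. This affects how the fix is carried out, not whether the gap exists.

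**Conclusion.** The point holds in conditional form. Nothing in the listed criteria or the household rule stops a control from living with a current recipient, and the SAP has no analysis that would show whether it matters. If such homes exist and benefit spills over, the expected bias is toward no effect.

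The size cannot be derived from the documents. With 1% to 10% of controls affected at half benefit, both assumed, power drops from 0.801 to between 0.797 and 0.759, a loss of about 0.4 to 4 points. At the low end this is negligible. The calculation also assumes equal groups, an unchanged SD and the SAP's total of 720. This is a minor, inexpensive improvement, not a demonstrated flaw in the trial.

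**What to change.** **While enrolment is open:** add an exclusion that applies to controls only, for anyone with a household member who currently receives peer support. One screening question is enough, unless the screening survey already asks it.

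**For controls already enrolled**, including those who joined before 22 February 2016: have each site compare control addresses with its own recipient list, or ask at the next scheduled contact. Record a yes/no flag for a shared home. Add to the SAP a sensitivity analysis that repeats the primary comparison without flagged controls, and report how many were flagged. That count alone replaces the assumed share f with an observed one.

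**Cost:** one question, a few lost control candidates, and some staff time at each site. The address check uses contact details of recipients who have not consented to the study, so it should be done at the site and return only the flag to the coordinating center. Removing flagged controls also takes out people who live with someone, so if many are flagged, the adjusted regression should be repeated alongside the unadjusted test.
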